10. REFERENCE LIST	
List of In-Text Tables	
Table 1. Prismocitrate 18	17
List of In-Text Figures	
Figure 1. University of Alabama at Birmingham Continuous Venovenous	
Hemodiafiltration Protocol	28
List of Appendices	
Appendix 1 Blood Sampling Schedule	66
Appendix 2 Schedule of Events	69
Annendix 3 Investigator's Signature	72

SYNOPSIS

Sponsor:

Baxter Healthcare Corporation

Name of Finished Product:

Prismocitrate 18

Name of Active Ingredient:

Prismocitrate containing 18 mmol/L trisodium citrate

Study Title:

Clinical Evaluation of Use of Prismocitrate 18 in Patients Undergoing Acute Continuous Renal Replacement Therapy (CRRT)

Study Number:

1407-004

Study Phase: III

Primary Objective(s):

The primary objective of this study is to evaluate the efficacy of Prismocitrate 18 in prolonging extracorporeal circuit life in patients treated with continuous renal replacement therapy (CRRT). The Control Group will be patients receiving CRRT with no anticoagulation.

Secondary Objectives:

The secondary objectives of this study are to:

- evaluate the efficacy of using Prismocitrate 18 in achieving appropriate anticoagulation through assessments of systemic and post-filter blood ionized calcium (iCa) concentrations,
- evaluate the efficacy of using Prismocitrate 18 in delivering the prescribed CRRT dose, with delivered dose based on total (daily) effluent volume and expressed as mL/kg/hour,
- evaluate the safety profile of Prismocitrate 18 through assessments of metabolic parameters (including serum bicarbonate, iCa, total calcium, total calcium/iCa ratio, magnesium, chloride, and other relevant serum electrolytes); anion gap, pH, base excess, bleeding events (number, location, duration); and the number and type of blood transfusions along with the number of units infused, and
- complete training on administration of Prismocitrate 18 and demonstrate the understanding of the user groups on how to use the solution by passing an assessment at the end of training.

Study Design:

This study is a multi-center, prospective, non-blinded, one to one randomized study. A total of 160 adult patients, 80 in each study arm, will be enrolled at up to 15 investigational sites in the United States and Canada. Patients meeting all of the inclusion criteria and none of the exclusion criteria of this protocol and deemed treatable by either CRRT with Prismocitrate 18 solution or CRRT with no systemic anticoagulation are eligible for enrollment in the study. If a patient is receiving standard-of-care CRRT, they must be randomized within 24 hours of initiation of their standard-of-care CRRT. All patients will be treated with continuous venovenous hemodiafiltration (CVVHDF) as the study CRRT modality. Patients enrolled in the study will receive either Prismocitrate 18 anticoagulation or no systemic anticoagulation during their CRRT, and the extracorporeal circuit life will be monitored for up to 120 hours of study CRRT (Treatment Period). During the Treatment Period, the adequacy of anticoagulation in the Prismocitrate 18 patients will be assessed by monitoring extracorporeal circuit pressures and by assessment of systemic and post-filter blood iCa concentrations. Patients will be monitored for acid-base parameters and serum electrolytes at baseline (prior to any CRRT), initiation (after randomization but before the initiation of study CRRT), at initiation of study CRRT and at predetermined intervals during treatment. Information on bleeding events (number, location, duration) and the number and type of blood transfusions along with the number of units infused will also be collected.

Study Population:

One hundred sixty (160) adult patients with AKI or other serious conditions who require CRRT are planned.

Inclusion/Exclusion Criteria:

Each patient must meet the following inclusion criteria to be enrolled in this study.

- 1. Patient or legally-authorized representative has signed a written informed consent form (ICF).
- 2. Patient must be receiving medical care in an intensive care unit (ICU) (eg, medical ICU, surgical ICU, cardiothoracic ICU, Trauma ICU, Mixed ICU, other).
- 3. Patient age \geq 18 years.
- 4. Adult patients with AKI or other serious conditions who require treatment with CRRT.
- 5. Patients are expected to remain in the ICU and on CRRT for at least 72 hours after randomization.
- Patients already receiving standard-of-care CRRT must be randomized within 24 hours of initiation of their standard-of-care CRRT.

Patients who meet any of the following exclusion criteria will not be enrolled in the study.

- 1. Patients requiring systemic anticoagulation with antithrombotic agents for reasons other than CRRT. The exception is patients receiving subcutaneous heparin for deep vein thrombosis prophylaxis according to institutional practice or patients on aspirin may be enrolled.
- 2. Patients in whom citrate anticoagulation is contraindicated such as patients with a known allergy to citrate or who have experienced adverse events associated with citrate products including patients with a prior history of citrate toxicity or patients with uncorrected severe hypocalcemia (whether in the context of current citrate administration or due to the underlying disease state).
- 3. Patients who are not candidates for CRRT.
- 4. Patients who are receiving extracorporeal membrane oxygenation (ECMO) therapy.
- 5. Patients with severe coagulopathy [ie, platelets < 30,000/mm3, international normalized ratio (INR) > 2, partial thromboplastin time (PTT) > 50 seconds] including severe thrombocytopenia (platelets < 30,000/mm³), HIT (heparin induced thrombocytopenia), ITP (idiopathic thrombocytopenia purpura), and TTP (thrombotic thrombocytopenia purpura) should not be enrolled in the trial.
- 6. Patients with fulminant acute liver failure or acute on chronic liver failure as documented by a Child-Pugh Liver Failure Score > 10.
- 7. Patients with refractory shock associated with persistent, worsening lactic acidosis (lactate > 4 mmol/L). However, patients with improving subsequent serum lactate levels may be enrolled.
- 8. Patients unlikely to survive at least 72 hours.
- 9. Female patients who are pregnant, lactating, or planning to become pregnant during the study period. Note: A female patient of childbearing potential, defined as a woman less than 55 years old who has not had partial or full hysterectomy or oophorectomy, must have a negative serum beta human chorionic gonadotropin (β-hCG) pregnancy test during the screening period (after consent and prior to randomization) and before CRRT treatment begins. A female patient of childbearing potential must use medically acceptable means of contraception during their participation in the study.
- 10. Patients who are currently participating in another interventional clinical study.
- 11. Patients with a medical condition that may interfere with the study objectives.

Test Product, Dose, and Mode of Administration:

Prismocitrate 18 (the investigational drug) is intended to be used as a replacement solution for regional anticoagulation of the extracorporeal circuit in patients undergoing continuous renal replacement therapy (CRRT). The renal replacement solution for regional anticoagulation containing 18 mmol/L citrate is

designed for pre-dilution infusion into the extracorporeal circuit before the blood pump (target blood citrate concentration of 3 to 5 mmol/L of blood).

Study Duration:

The anticipated duration of the clinical trial is approximately 4 years from the first patient enrolled to the last patient complete.

Individual patients will participate in the study for up to 35 days with a study treatment period of up to 120 hours of study CRRT post-randomization. At the conclusion of study treatment, patient adverse events and serious adverse events will be collected for a period of 30-days.

Efficacy Assessments:

Primary Efficacy Endpoint:

The Prismaflex M150 Set extracorporeal circuit life will be assessed over a maximum of 120 hours by the duration of time for which each Prismaflex M150 Set can be used continuously over a maximum 72 hour timeperiod in each patient. The Prismaflex M150 Set will be replaced any time study CRRT is stopped during the Treatment Period (regardless of duration) or any time a circuit is used for 72 continuous hours (ie, "Advisory Time to Change Set"). The end of the extracorporeal circuit life will be defined by the occurrence of one or both of the following Prismaflex® System alarms/conditions if the alarms cannot be mitigated. At this point, study CRRT will be terminated and the extracorporeal circuit replaced because mitigation of the following alarms is not possible:

- "Warning: Filter Clotted", and/or
- "Advisory TMP Too High"

Secondary Efficacy Endpoints:

Systemic and post-filter blood iCa concentrations will be assessed at baseline (systemic only), initiation (systemic only), 1 hour and every 6 hours during the 120 hour Treatment Period and at 120 hours or end of the Treatment Period from the initiation of study CRRT in each patient as indications of both the extent of calcium chelation prior to the CRRT filter and calcium restoration after the CRRT filter. Post-filter iCa will only be measured in the Prismocitrate 18 arm.

Delivery of the prescribed CRRT dose will be based on the patient's weight and daily recordings of the effluent volume (in mL). These data will be used to calculate delivered dose (mL/kg/hour).

Safety Assessments:

Safety endpoints include:

- 1. Serum bicarbonate and pH, will be measured at baseline, at initiation of study CRRT and every 6 hours from the initiation of study CRRT during the 120 hour Treatment Period and at 120 hours or end of the Treatment Period.
- 2. Blood total calcium concentrations will be measured at baseline, at initiation of study CRRT 1 hour and every 6 hours from the initiation of study CRRT during the 120 hour Treatment Period and at 120 hours or end of the Treatment Period from the initiation of study CRRT.
- 3. Serum electrolytes (sodium, potassium, chloride, phosphate, and magnesium) will be measured at baseline, at initiation of study CRRT and every 6 hours from the initiation of study CRRT during the 120 hour Treatment Period and at 120 hours or end of Treatment Period.
- 4. As indicators of citrate accumulation (along with pH), the total calcium/iCa ratio (both measurements in mmol/L) will be measured at baseline, at initiation of study CRRT, 1 hour and every 6 hours from the initiation of study CRRT during the 120 hour Treatment Period and at 120 hours or end of Treatment Period. Anion gap and base excess will be measured at baseline, at initiation of study CRRT and every 6 hours from the initiation of study CRRT during the 120 hour Treatment Period and at 120 hours or end of Treatment Period.
- 5. The number, location and duration of bleeding events during the 120 hour Treatment Period will be collected. If a blood transfusion is needed during the 120 hour Treatment Period, the number and type of transfusions along with the number of units infused will be collected.

- Change from baseline to final measurement in laboratory and vital signs measurements will be collected.
- 7. The incidence of adverse events and serious adverse events from the time the patient signs the informed consent form (ICF) until 30-days post study CRRT treatment (end of study) will be collected.

Analysis of Training on Administration of Prismocitrate 18

The site level user groups will be trained on the use of Prismocitrate 18 in CRRT and their understanding assessed prior to use in the clinical trial setting. The user groups will be comprised of physicians, nurses, and other clinicians who may be part of prescribing, initiating, or modifying treatment during the 120 hour Treatment Period. A descriptive summary of training results on administration of Prismocitrate 18 will be provided in the Clinical Study Report following completion of the study.

Statistical Methods:

The Statistical Plan for the study can be found in Section 8.

Date of Original Approved Protocol: 2016 FEB 08 Date of Approved Amendment 1: 2016 MAY 20 Date of Approved Amendment 2: 2017 JAN 05 Date of Approved Amendment 3: 2018 FEB 08

LIST OF ABBREVIATIONS AND DEFINITIONS OF TERMS

ABBREVIATION	DEFINITION
ABG	arterial blood gases
ADR	adverse drug reaction
AE	adverse event
AKI	acute kidney injury
ALP	alkaline phosphatase
ALT	alanine transaminase
ANCOVA	analysis of covariance
APACHE II	Acute Physiology and Chronic Health Evaluation II classification system
AST	aspartate transaminase
β-hCG	serum beta human chorionic gonadotropin
BFR	blood flow rate
BUN	blood urea nitrogen
Ca ²⁺	calcium
CFR	Code of Federal Regulations
CRRT	continuous renal replacement therapy
СТ	computerized tomography
CTA	Clinical Trial Application
CVVHDF	continuous venovenous hemodiafiltration
DMC	data monitoring committee
eCRF	electronic case report form
EDC	electronic data capture
FA	full analysis set
FDA	Food and Drug Administration
g/dL	grams per deciliter
GCP	Good Clinical Practice
GMP	Good Manufacturing Practice
GPS	Global Patient Safety
HD	hemodialysis
HIPAA	Health Insurance Portability and Accountability Act
ICF	informed consent form
iCa or iCa ²⁺	ionized calcium

ABBREVIATION	DEFINITION
ICU	intensive care unit
ICH	International Conference on Harmonization
IFU	Instructions For Use
IND	Investigational New Drug
INR	international normalized ratio
IP	investigational product
IRB	institutional review board
IV	intravenous
kg	kilogram
L	Liter
MedDRA	Medical Dictionary for Regulatory Activities
mEq	milliequivalent
mg	milligram
mL	milliliter
mmHg	millimeter of mercury
mmol	millimole
MMRM	mixed-effects model repeated measures
mOsm	milliosmol
PBP	pre-blood pump
PI	principal investigator
PP	per protocol set
PT	prothrombin time
PTT	partial thromboplastin time
Q _B	blood flow rate (real blood flow pumped out of the patient)
Q_{D}	dialysate rate
QE	effluent rate
QFR	fluid removal rate
Q _{PBP}	pre-blood pump infusion rate
QR	replacement fluid rate
RCA	regional citrate anticoagulation
REB	research ethics board
RRT	renal replacement therapy
SAE	serious adverse event

ABBREVIATION	DEFINITION	
SAP	statistical analysis plan	
SAS	Statistical Analysis Software	
SOC	system organ class	
SUSAR	Suspected Unexpected Serious Adverse Reaction	
TMP	transmembrane pressure (mmHg)	
US	United States	
VBG	venous blood gases	

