8.3 Analysis Populations

The Full Analysis (FA) Set will include all randomized patients who received any study treatment for any period of time.

All analyses will be performed on the FA Set unless otherwise noted.

In addition to the FA Set, a Per Protocol (PP) Set will be used to check the robustness and validity of the primary analysis by repeating the analysis on the PP Set as a sensitivity analysis.

The PP Set defines a subset of the FA Set including patients who:

- fulfill all inclusion criteria.
- do not meet any of the exclusion criteria.
- were randomized and treated according to the randomization scheme.
- received at least 80% of their prescribed CRRT dose.
- do not have major protocol deviations that might impact the assessment of the primary endpoint (eg, mechanical malfunction of the machine).
- have available survival data for extracorporeal circuit life of at least one circuit
 (ie, time to occurrence of Prismaflex System alarms/conditions as outlined in
 Section 6.7.1 Primary Efficacy Endpoint and alarm cause determined and
 confirmed by Independent Adjudicator as outlined in Section 9.9 Primary
 Endpoint Adjudication, or censored circuit life if no system alarms/conditions
 occurred until the circuit was used for 72 continuous hours or if CRRT was
 stopped during the Treatment Period for reasons other than system
 alarms/conditions or if Independent Adjudicator did not confirm the alarm cause).

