6.3 Protocol Deviations

Protocol Deviations will be classified as major and minor deviations.

Subjects with any major protocol deviation that may impact the primary endpoints will be excluded from the per-protocol analysis set, including but not limited to the following:

- Violations of inclusion and/or exclusion criteria
- Use of prohibited medication known to influence the primary endpoint
- Randomization or treatment errors
- Improper administration of study product
- Improper assessment of the primary endpoint
- Any other protocol deviations that may impact the primary endpoints

Frequencies of protocol deviations will be presented by study site and across all study sites on a deviation as well as on a subject basis.

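### Exclusion 9 defines childbearing potential so that a woman with a partial or one-sided oophorectomy is exempt from the pregnancy test and the contraception duty

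*Protocol*

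**What the plan says.** Exclusion 9 is worded the same in the Protocol Synopsis, Protocol Section 4.3 and SAP Section 6. It has three parts.

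- **The exclusion itself:** "Female patients who are pregnant, lactating, or planning to become pregnant during the study period".
- **A note requiring a negative serum beta-hCG test** of a woman of childbearing potential, "defined as a woman less than 55 years old who has not had partial or full hysterectomy or oophorectomy". The test falls "during the screening period (after consent and prior to randomization) and before CRRT treatment begins".
- **A contraception duty tied to the same definition:** "A female patient of childbearing potential must use medically acceptable means of contraception during their participation in the study".

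Inclusion 6, in the same three places, bears on the timing: "Patients already receiving standard-of-care CRRT must be randomized within 24 hours of initiation of their standard-of-care CRRT". Protocol Section 7.2 allows screening for up to 96 hours before randomisation and expects most subjects to screen and randomise within 24 hours.

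**The concern.** The test is there to find pregnancies that nobody yet knows about. The definition decides who gets it, and it releases any woman under 55 with a listed operation, even if only part of the organ was removed. Removing one ovary, or part of one, does not by itself rule out pregnancy in a woman who still has a uterus. The rule therefore exempts some women whom the exclusion is meant to protect. At stake is an unrecognised pregnancy exposed to study treatment, not the efficacy comparison. The protocol treats pregnancy as important: Section 4.4 lists it as a reason for withdrawal, and Section 6.10.2 counts fetal death, congenital abnormality and abortion among the serious adverse event criteria.

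The timing phrase raises a smaller question. Some patients enter the trial already on CRRT, and the criterion asks for a test before CRRT treatment without saying which CRRT it means.

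**Working it through.** The plan states no figure on this point, so there is none to reproduce. The check is a reading of the text and one timeline.

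**1. Who falls outside the definition.** The wording can be parsed in two ways.

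- *Partial and full both qualify oophorectomy.* A partial oophorectomy then removes a woman from the definition in so many words.
- *Partial and full qualify hysterectomy only.* The bare word oophorectomy remains. Nothing says that both ovaries must have been removed, so a one-sided operation still exempts.

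On either parsing, a woman under 55 with a uterus and remaining ovarian tissue can be outside the definition.

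**2. What she is exempt from.** The beta-hCG test and the contraception duty both apply only to women who meet the definition, so she is released from both. The opening sentence of exclusion 9 still applies to her, but in practice it works only if the pregnancy is already known.

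**3. The timing phrase.** Inputs, with randomisation at 0 h:

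- earliest screening after consent: −96 h (Section 7.2)
- earliest permitted start of standard-of-care CRRT: −24 h (inclusion 6)
- screening time that can precede even that earliest start: 96 − 24 = 72 h

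| Meaning of CRRT treatment in exclusion 9 | When the patient consents | Can the timing be met? |
|---|---|---|
| Study CRRT | Any time before randomisation | Yes. A test before randomisation already precedes study CRRT, so the phrase adds nothing |
| Any CRRT | Before standard-of-care CRRT starts | Yes, if tested between consent and that start |
| Any CRRT | After standard-of-care CRRT starts | No |

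Only the last row is impossible.

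**4. Does usage elsewhere settle the meaning?** Not fully. Section 5.2 uses CRRT alone for the study treatment but adds that it is post-randomisation. Where the same section defines baseline, it says explicitly that it means any CRRT. Exclusion 9 carries neither qualifier.

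**5. Does a pre-consent result help?** Section 7.2 lets sites enter standard-of-care data taken before consent, with laboratory results limited to 24 hours. That allowance covers the items listed in Section 7.3. Neither that list nor Appendix 1 names beta-hCG, and exclusion 9 itself asks for a test after consent. Section 7.2 is therefore not a clear way round the last row.

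**The case against.** The strongest reply is that the opening sentence of exclusion 9 bars every pregnant woman whatever her surgical history, and that the note sets a minimum and does not forbid testing others. Both statements are true. They limit the gap but do not close it, because the required test is the only stated means of finding an unknown pregnancy and these women are exempt from it. It is also fair to say that the documents nowhere state that such women can conceive. That is general medical knowledge, and the point depends on it.

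On timing, much of the reply stands. The documents often use CRRT alone for study CRRT, and on that reading every patient can comply. A reader might infer from inclusion 6 that patients who enter on CRRT cannot meet the test timing at all. The documents do not support that. It requires both the any-CRRT meaning and consent after standard-of-care CRRT began. Section 7.2 expects most subjects to screen and randomise within 24 hours, so that group need not be rare, but no proportion is given and any count of affected patients would be guesswork.

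A reader might also infer that a mistimed test removes a patient from the Per Protocol Set, which requires that patients "do not meet any of the exclusion criteria", while SAP Section 6.3 lists "Violations of inclusion and/or exclusion criteria" among the deviations that lead to removal. This is not established. The excluded states are pregnancy, lactation and planned pregnancy, and the test timing sits in a note. SAP 6.3 is directed at major deviations that may affect the primary endpoint. The Per Protocol Set serves only as a sensitivity analysis.

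Finally, beta-hCG has no row in Appendix 1, Appendix 2 or SAP Tables 1 and 2. A reader might infer that nothing records compliance, but Section 7.3 item 3 already puts the eligibility criteria on the eCRF. What is missing is detail: the result and time of the test.

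**Conclusion.** The definition gap holds on the text, on either parsing. Following exclusion 9 as written, a woman under 55 with a partial or one-sided oophorectomy and a uterus can be randomised without a pregnancy test and without the contraception duty. Probably very few patients are affected. The documents give no figure, and *very few* is a judgement. The consequence for any one of them could be grave, so the wording should be corrected even though the numbers are small. The conclusion rests on one assumption from outside the documents: that pregnancy remains possible with a uterus and some ovarian tissue.

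The timing phrase is ambiguous, not unworkable. It conflicts with inclusion 6 only if it means any CRRT, and then only for patients first consented after standard-of-care CRRT began.

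Neither part touches sample size, power, alpha or the primary analysis on the Full Analysis Set.

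**What to change.** - **Definition.** In exclusion 9, in the Synopsis, Protocol Section 4.3 and SAP Section 6, reword the surgical exemption so that it covers only surgery after which pregnancy is not possible. State that a partial or one-sided oophorectomy does not exempt.
- **Timing.** The sponsor should say which CRRT exclusion 9 means and reconcile it with inclusion 6 and with the screening and pre-consent data rules in Section 7.2, in both the Protocol and the SAP. Which timing rule is right is for the sponsor to decide.

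The cost is a wording amendment to both documents. A very few more women would have a test that is already required of others, and would come under the contraception duty. No analysis changes.
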